**Objectives:** To assess changes in visual acuity (primary outcome) and contrast sensitivity (secondary outcome) and to determine the feasibility of and to develop expertise in measuring BDNF in human blood samples (tertiary outcome). **Rationale:** Animal and human studies examining the effects of exercise on cognition and peripheral nerve regeneration demonstrate that circulating BDNF levels vary with outcome; whether BDNF varies with exercise levels is less well studied. If amounts of exercise and circulating BDNF levels similarly co-vary in humans and in mice, BDNF may be useful as a biomarker for testing exercise regimens as interventions in human studies. Additionally, no human studies have monitored exercise, BDNF, and retinal and visual outcomes. **Design:** The study is comprised of a 12-week exercise portion with one return visit 3 months after the end of the exercise portion. Participants will be recruited from our volunteer database, which includes elderly individuals (65-89 years old) who are not visually impaired and who report being sedentary (defined as engaging in structured physical activity for 30 minutes or less over the last 3 months) and who meet other inclusion criteria previously established for our exercise studies. Participants will be divided into a group that will exercise and a group that will remain sedentary. Exercising participants will train three times a week for 12 weeks on a stationary bicycle ergometer ("spin" training). Exercise intensity will begin at low levels (50% of maximal heart rate reserve) and will be increased by 5% every week (as tolerated by the participant) to a maximum of 80% of maximal heart rate. Exercise time will progress from an initial 20 minutes per session to a maximum of 45 minutes by increasing 5 minutes each week. A CPR-certified fitness specialist will monitor each session. We will follow the guidelines provided by the American College of Sports Medicine for optimizing cardiovascular fitness. Blood draws and visual assessments will be taken at one week prior to the 12-week regimen, at the 3-month follow-up, and at weeks 1, 4, 8, and 12 of the 12-week regimen. Blood will be drawn by a certified phlebotomist in the rest period before the exercise, immediately following the exercise, and after a recovery period of 10 min. Visual assessment will include visual acuity and contrast sensitivity (CSV-1000E). Control (non-exercising) participants will have blood drawn and undergo other assessments identically to the exercised participants. To control for potential benefits of the spinning program that are unrelated to aerobic exercise, they will participate in group balance training. All participants will be instructed to otherwise continue with their daily routines and will be contacted bi-weekly to track self-reported levels of physical activity outside of the study. All participants will be asked to return to their pre-study routines following the 12-week exercise portion of the study. All procedures involving human subjects have been reviewed and approved by an Institutional Review Board (IRB). Sample remainders will be archived for analyses that are beyond the scope of a SPiRE support. **Expected outcomes and Significance:** If functional changes differ between exercised versus control cohorts across the study period, we will conclude that even relatively short-term aerobic exercise can be beneficial to visual health. Such an outcome would also suggest that effects are due to physiological mechanisms rather than test-specific psychological confounds. Circulating levels of BDNF will be measurable and will increase in exercised versus unexercised subjects, indicating that circulating BDNF levels correlate with exercise activity. **Potential difficulties and alternative approaches:** (1) It may be that changes in BDNF levels are not observed. Human studies demonstrate that many forms of aerobic exercise, including "spin" ergometer training, increase circulating BDNF levels. However, the temporal relationship between an exercise session and its effects on BDNF may vary. If we do not observe changes in BDNF with the proposed sampling regimen within the first week of the 12-week training portion of the study, we will add a draw at the midway point of the spin session. Additional draws during the recovery period at 5 min intervals may be attempted (we have institutional approval, though these would require cannulation, which increases complexity and increases the probability of participant drop-out). Additions will be iterative and kept to a minimum based on assaying for BDNF concentration the day of the spin sessions. (2) It may be that that BDNF levels do not vary with exercise volume changes. If so, similar to the suggested alternative in Aim 1, additional circulating growth factors will be assessed. Candidates include insulin-like growth factor 1 (IGF-1), vascular endothelial growth factor (VEGF), and leukemia insulin factor (LIF), nerve growth factor (NGF), and Neurotrophin-4/5.

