
## Methods

### *Visual function testing:*

**Visual acuity:** The visual acuity of the subjects will be measured according to a standard procedure developed and used by many multi-center clinical trials. An Early Treatment Diabetic Retinopathy Study (ETDRS) Chart and a 3 meter testing lane providing standardized chart illumination (80 to 120 cd/m^2) are used to test visual acuity. Testing is done at a distance of 3 meters (20 feet) or (for subjects with sufficiently reduced vision) a distance of 1 meter. The 3 meter distance should be marked clearly and permanently while the 1 meter distance must be measured with a 1 meter string. Subjects should be prevented from seeing the chart until the visual acuity testing actually begins.

The subject is first positioned at 3 meters in a chair with his or her back firmly touching the back of the chair. The head of the subject should not move forward or backward during the test so that the subject's eyes remain at the specified distance. The subject is instructed to slowly read with the study eye(s) each letter of each line at a rate not faster than about one letter per second. If the subject is unable to correctly identify all the letters of the top two lines, then position the subject at 1 meter and again instruct the subject to read each letter of each line beginning again with the top line. If the subject loses his or her place the examiner may point to a line (but outside the line at the edge of the chart) or below the letter (at a distance equal to the inter-letter spacing in a line) with a long pointer. The testing procedure for visual acuity is based on the principle that the objective is to test resolution ability and not the ability to find each letter on a line.

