The subject's responses are recorded on the visual acuity recording sheet. Each wrong response is scored by putting an X through the letter and writing the incorrect response above the letter. Once a subject has identified a letter with a definite single-letter response and has read the next letter, a correction of the previous letter cannot be accepted. If the subject changes a response before s/he has read aloud the next letter, then the change should be accepted. When the subject has missed at least 3 letters on the previous line and can make no further meaningful guesses, despite urges to read or guess, the examiner should stop the test for that eye. The examiner records the number of letters correctly read and from this number computes the Snellen Equivalent and LogMAR values from the table provided.

**Script: This is a visual acuity test like you might have seen at your doctor's office. This chart shows letters that become smaller toward the bottom. I want you to stop at the end of each row and wait until I ask you to continue. Please try your best to read all the letters. If you are unsure, I will ask you to take a guess even if it is very difficult for you to see. Any questions?**

**Statistical analysis:** The number of correct ETDRS responses from a subject assessed prior to start of the first session of the the 12 week study is subtracted from the number of correct responses elicited at the end of the last session of the study. The means of these differences for each study group (Balance Training vs Aerobic Exercise) is compared by two-tailed t-test.

**Contrast sensitivity:** The contrast sensitivity of the subjects will be measured with the Pelli-Robson Chart following the instructions provided with the chart. The two sides of the Pelli-Robson Chart have different letter sequences but are otherwise identical. The chart should be illuminated as uniformly as possible, so that the luminance of the white areas is between 80 and 120 cd/ m^2 with no glare. The patient should sit directly in front of the chart at a distance of 1 meter (use the same 1 meter string as for visual acuity testing to measure the eye-to-chart distance). Subjects should be prevented from seeing the chart until the contrast sensitivity testing actually begins. Subjects should wear their best distance correction.

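### The primary t-test on change in raw ETDRS letter count forgoes a modest precision gain from baseline adjustment, and puts 3 m and 1 m counts on one scale

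*Combined protocol and SAP*

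**What the plan says.** Visual acuity is the primary outcome (Objectives). Under Visual acuity, Statistical analysis, the count of correct letters before the first session "is subtracted from the number of correct responses elicited at the end of the last session of the study", and the analysis is: "The means of these differences for each study group (Balance Training vs Aerobic Exercise) is compared by two-tailed t-test". No covariate or model is named.

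On allocation, the Design text says only: "Participants will be divided into a group that will exercise and a group that will remain sedentary". It does not mention randomisation.

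The testing procedure under Visual acuity allows two distances. "If the subject is unable to correctly identify all the letters of the top two lines, then position the subject at 1 meter", and the examiner must then "again instruct the subject to read each letter of each line beginning again with the top line". The examiner also "computes the Snellen Equivalent and LogMAR values from the table provided", but the analysis paragraph uses the count and not these derived values. Nothing adds a distance constant, credits letters read at 3 m, or requires the same distance at both visits. The longer distance is itself given in two units that disagree: "Testing is done at a distance of 3 meters (20 feet)".

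**The concern.** Baseline acuity is collected on everyone but enters only by subtraction, which fixes its coefficient at 1. When the groups are comparable at baseline, estimating that coefficient gives a smaller standard error from the same data.

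The second issue is the scale. A letter seen from 1 m subtends three times the angle it does from 3 m, so the same eye reads more letters at 1 m. If a subject is tested at 3 m at one visit and 1 m at the other, the difference in counts mixes change in acuity with change in distance. The sign can be wrong: a subject who worsens enough to be moved to 1 m is scored as improving, and one who improves enough to return to 3 m is scored as worsening. In a small arm, one such value shifts the mean and widens the standard error of the primary comparison.

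**Working it through.** The documents give no sample size, standard deviation, correlation or dropout rate, so there is no stated figure to reproduce. The correlations, arm sizes, standard deviations and chart properties below are assumptions.

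**Baseline adjustment.** Let r be the baseline-to-final correlation, with equal variances s² at the two visits and comparable groups.

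- Change-score variance: 2(1 − r)s². ANCOVA residual variance: (1 − r²)s². Ratio: (1 + r)/2.
- r = 0.6 gives 0.80 and r = 0.9 gives 0.95, so variance is 20% to 5% lower. The t-test standard error is wider by 1/√0.80 = 1.118 to 1/√0.95 = 1.026, that is 12% to 3%.
- With n per arm, estimating the slope multiplies the ratio by 1 + 1/(2n − 4):

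| n per arm | Multiplier | Ratio, r = 0.6 | Ratio, r = 0.9 | ANCOVA variance gain |
|---|---|---|---|---|
| 10 | 1 + 1/16 | 0.850 | 1.009 | 15% to nil (−1%) |
| 20 | 1 + 1/36 | 0.822 | 0.976 | 18% to 2% |
| 30 | 1 + 1/56 | 0.814 | 0.967 | 19% to 3% |

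If the groups differ at baseline, the two estimates differ by (1 − r) letters per letter of imbalance: 0.4 at r = 0.6 and 0.1 at r = 0.9.

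**Distance offset.** Moving from 3 m to 1 m changes the angular size by log10(3) = 0.477 log units. At an assumed 0.02 logMAR per letter this is 0.477/0.02 = 23.9 letters.

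This is an upper value, because the chart has a last line. Assume 14 lines of 5 letters (70 letters), with the top line at logMAR 1.0 from 3 m. A subject at logMAR 0.0 reads 11 lines, or 55 letters, at 3 m and can gain at most 70 − 55 = 15 at 1 m. At logMAR 0.1 the maximum is 70 − 50 = 20. At 0.2 there are 25 letters left, so the full 23.9 applies.

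**Wrong sign.** A subject who reads 10 letters at 3 m at baseline and would read 9 at the end is moved to 1 m and scored 9 + 23.9 = 32.9. The recorded change is 32.9 − 10 = +22.9 for a true change of −1.

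**Effect of one switch with no true change.** For an offset D, the arm mean shifts by D/n and that arm's expected sample variance becomes s² + D²/n, where s is now the SD of change. The standard error of the comparison is multiplied by √[(2s² + D²/n)/(2s²)]. The last two columns run from s = 8 to s = 4 letters.

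| n per arm | Mean shift, D = 15 | Mean shift, D = 23.9 | SE wider, D = 15 | SE wider, D = 23.9 |
|---|---|---|---|---|
| 10 | 1.5 | 2.4 | 8% to 31% | 20% to 67% |
| 20 | 0.75 | 1.2 | 4% to 16% | 11% to 37% |
| 30 | 0.5 | 0.8 | 3% to 11% | 7% to 26% |

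These figures describe what one switch does. They say nothing about how often one occurs.

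**Stated distance.** 20 feet is 20 × 0.3048 = 6.1 m, not 3 m, and a fixed offset depends on which distance is used.

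**The case against.** The change-score t-test is pre-specified, two-sided and matches an objective worded in terms of change. Under random allocation it is unbiased, and the precision it gives up is small. With about 10 per arm and a correlation near 0.9 it gives up nothing. All of this stands. If allocation is not random, the real gap is the allocation method, and ANCOVA does not close it. That also stands.

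On distance, the protocol reserves 1 m for subjects with sufficiently reduced vision, yet recruits people without visual impairment. A switch needs failure on the two largest lines at one visit and not the other. The worked case of 10 letters falling to 9 describes someone who can barely read those two lines at 3 m, and so is unlikely to be enrolled. These points limit how often the problem can arise, but do not make the two counts comparable.

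A reader might infer that one slip of the tongue sends a subject to 1 m, because the scoring rule says that once a subject "has read the next letter, a correction of the previous letter cannot be accepted". The literal text allows this. But the trigger is worded as inability, and a response changed before the next letter is read is accepted, so frequent accidental switching cannot be inferred. A slip by someone with good acuity is also where the end of the chart holds the error nearer 15 letters than 24.

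The conversion table and recording sheet are not in the documents and may already handle distance. That could make LogMAR safe to analyse, but it does not help a test run on the count.

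**Conclusion.** The point holds as two refinements to a valid primary test.

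The baseline gain is modest and conditional on comparable groups and on the assumed correlations. The distance effect is confined to subjects whose test distance differs between the two visits. Subjects tested at one distance throughout are essentially unaffected, apart from any ceiling at 1 m. For a subject who does switch, the spurious change is up to about 24 letters, or about 15 for good acuity on the assumed chart.

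Three stronger readings are not supported:

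- **The t-test is invalid or biased.** Nothing in the plan makes it so under random allocation.
- **Switching is likely to distort the trial result.** No frequency is given or derivable, and the population makes switches rare.
- **A switch always exceeds any plausible real change.** The documents give no range of plausible change to compare it with.

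The case for acting rests on the low cost and on removing a possible wrong-sign error from the primary endpoint.

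**What to change.** 1. State whether allocation is random. If it is, make ANCOVA of final acuity on arm and baseline acuity the primary analysis, with the change-score t-test as a sensitivity analysis. If it is not, report both, since they can estimate different quantities and neither removes confounding.
2. Reconcile the metre and foot figures for the longer distance before fixing any conversion.
3. Name a distance-corrected score as the analysed variable. This can be LogMAR, which is already computed for each test, once the table is confirmed to account for test distance. Alternatively, use letters with a fixed offset between the two distances.
4. Record the test distance at each visit, if the recording sheet does not already do so.

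The cost is one degree of freedom, at most one recorded field, a check of the table and slightly more analysis work. With about 10 per arm and a correlation near 0.9, step 1 brings no precision gain.
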